10.4.5 Efficacy Evaluation

The primary analysis of efficacy data will be performed on the ITT population. Additionally, for the main efficacy variable, a supportive analysis using mITT and PP populations will be carried out.

The primary endpoint (time from the first study treatment intake (T_0)) to recovery defined as 1st formed stool followed by a nonwatery stool (in hours), will be analysed using a time to event methodology.

Time to event data will be analysed by using survival methods. The results will be presented both in summary tables and graphically in Kaplan-Meier plots and the estimated medians and quartiles will be provided.

The comparison between the 2 groups of treatment will be performed using Gehan-Wilcoxon test. Subject prematurely withdrawn or ending the study without recovery will be censored (not responder).

Sensitivity analyses will be conducted to further explore the primary efficacy endpoint adjusting by country.

A cox model [14] will be used to assess the impact of other factors like season of randomisation, absence/presence of faecal pathogens on the treatment effect.

The analysis regarding secondary efficacy endpoints will be performed on the ITT population; supportive analysis using PP population will be carried out.

The secondary efficacy variables are:

- a) Abdominal pain intensity per 12-hour period.
- b) Time (hours, minutes) from diarrhoea onset to recovery defined as 1st formed stool followed by a nonwatery stool.
- c) Time (hours) from first watery stool to the first formed stool.
- d) Time (hours) from the 1st study treatment intake to the last watery stool.
- e) Number of stools, per 12-hour period.
- f) Number of watery stools, per 12-hour period.
- g) Percentage of subjects with associated symptoms such as nausea, vomiting, abdominal pain and anal irritation, per 12-hour period.

Missing data of secondary efficacy variables will not be replaced.

The secondary endpoints related to time to event (efficacy variables b, c and d) will be analysed using the same methodology as for the primary efficacy endpoint.

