1.2.1 Study population

854 subjects will be randomised to one of the two treatment groups (either active or placebo) at a ratio of 1:1 (i.e. 427 per treatment group). It is planned to recruit subjects in 90 centres in 7 countries, including Algeria, Czech Republic, Egypt, Lebanon, Poland, Romania and Tunisia.

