1.3.2.2 Safety assessments

Adverse Events (AEs)

AEs will be monitored from the time that the subject gives informed consent and throughout the study until 7 days after the end of study treatment

Physical Examination

Physical examinations, including body weight (kg) and body height (cm), will be conducted at Baseline (Visit 1), at Visit 2 and at Visit 3 if applicable. Height will be measured at Baseline only.

Any clinically significant physical examination findings (abnormalities) observed during the study will be reported as AEs. Any physical examination findings

(abnormalities) persisting at the end of the study will be followed by the investigator until resolution or until reaching a clinically stable endpoint.

Vital Signs

Blood pressure (mmHG) and heart rate (bpm) will be recorded after five minutes rest in sitting position at baseline (Visit 1) and each post-baseline visit, as well as body temperature (in °C using an oral/rectal/axillary/auricular/forehead/temporal thermometer).

1.3.2.3 *Other assessments*

Demographic data (date of birth and sex), medical and surgical history, including ongoing medical conditions, prior medications for acute diarrhoea episode as well as other prior medications will be collected at first visit.

A history of current acute diarrhoea episode will also be recorded, including:

- Date and time (hours, minutes) of first unformed loose or watery stool,
- Number of stools including number of unformed loose or watery stools, for each 12h period during the last 24 hours,
- Presence of other associated symptoms for the last 24 hours: nausea, vomiting, abdominal pain, anal irritation.

One faecal sampling for microbiological examination will be collected as soon as possible after inclusion for microbiological laboratory testing (for virology, bacteriology and parasitology testing) in order to determine the microbiological status of this acute diarrhoea episode, i.e. the absence/presence of the following faecal pathogens:

Virology testing:

- Rotavirus,
- Adenovirus,
- Norovirus.

Bacteriology and parasitology testing:

- Enteropathogenic and Enterotoxigenic Escherichia Coli (E. coli),
- Staphylococcus aureus,
- Shigella,
- Salmonella,
- Campylobacter,
- Yersinia enterocolitica,
- Amoebiasis (entamoeba histolytica),
- Giardia / lamblia.

1.3.2.4 *Withdrawal/discontinuation*

In case of either:

- impaired general health condition
- and/or moderate or severe dehydration
- and/or fever above 38°C

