1.3.4 Planned sample size

Assuming a median time to recovery of 55 hours in the active group and 70 hours in the placebo group (corresponding to a difference of 15 hours as evidenced in the Khediri et al study [1]), 363 evaluable subjects per treatment group (726 in total) will be required in order to detect such a difference using a two-sided Gehan-Wilcoxon test at a significance level of 5% and a power of 80%.

It is assumed a maximum of 5% of subjects prematurely withdrawn without recovery and a maximum of 10% of non-evaluable subjects (because of poor/incomplete diary completion). Accordingly, 854 subjects (427 per treatment group) will be required in order to achieve an 80% power.

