(f) Sensitivity analysis – recovered patients without recovery confirmation.

For patients whose last stool is a formed stool without any other subsequent stool to allow the confirmation of the recovery will be considered having recovered. This new endpoint will be analysed using the same methodology as for the primary efficacy endpoint on the ITT set.

(g) Baseline prognostic factors

The same subgroup analysis will be performed for the following baseline variables: Season of randomisation, Absence/Presence of faecal pathogens (virology, bacteriology and parasitology testing), Time since diarrhoea onset.

Cox analyses to assess the impact of baseline prognostic factors

A multivariate analysis of the time-to-recovery will be performed in order to take into account prognostic factors. A Cox proportional hazards model [2] will be performed to estimate the HR and its two-sided 95% CI.

The factors included in this analysis will include but will not be limited to (see section 3.2.18 for the parameterization):

Table 2 Prognostics factors for the Cox model analysis

Covariate	Categories
Time since diarrhoea onset	≤ median (reference) > median
Number of watery stools during the last 24 hours prior inclusion	Not applicable.
Country	Algeria, Czech Republic, Egypt, Lebanon, Poland, Tunisia (largest country to be used as reference)
Season of randomisation	Winter (reference), Summer.
Absence/presence of faecal pathogens for Virology testing	Positive (Rotavirus or Adenovirus or Norovirus) (reference), Negative (None) Not done/missing
Absence/presence of faecal pathogens for Bacteriology testing	Positive (Enteropathogenic or enterotoxigenic E. Coli or Staphylococcus aureus or Shigella or Salmonella or Campylobacter or Yersinia enterocolitica) (reference) Negative (None) Not done/missing
Absence/presence of faecal pathogens for Parasitology testing	Positive (aemibiasis or Giardia/lamblia) (reference), Negative (None) Not done/missing.

Since it is an exploratory search, other covariates may be added.

Step1:

Each of the potential factors associated with recovery listed in Table 2 together with the treatment variable will be tested in separate Cox proportional hazards models. Any factors found to be significant at $p \leq 0.20$ (via the Wald chi-square test statistic)

will be considered to be potentially important. The association between each covariate and treatment will be further explored by presenting separate KM plots for each level of the covariate.

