For this selection, the following SAS® code will be used:

```
CCI  
[REDACTED]  
[REDACTED]  
[REDACTED]  
[REDACTED]
```

Step2:

In a second step, each pre-selected parameter will be tested with the other retained parameters at the 0.001 level to confirm that there is no strong link between them. For continuous variables the Pearson correlation will be tested. For a mix of categorical and continuous variables Spearman's correlation coefficient will be used and for categorical variables a Chi2 test will be used. If the independence is not met for two parameters ($p < 0.001$) or $r \geq 0.5$, the choice will be done according to clinical and statistical relevance.

Step3:

All selected parameters will be entered into a multivariate Cox model. The stepwise variable selection method in the SAS® procedure PHREG will be performed with $p=0.20$ to enter variables in the model, and $p=0.15$ to remove variables from the model, to select the best model, in addition to the treatment variable which will be included in the model.

Tied events will be handled with the Exact method:

```
CCI  
[REDACTED]  
[REDACTED]  
[REDACTED]  
[REDACTED]  
[REDACTED]  
[REDACTED]
```

The interaction of each remaining term in the multivariate model with treatment will also be investigated. This will be done by adding interaction terms to the model. If there is evidence of any interaction with treatment (according to the p-value of the likelihood ratio test statistic obtained with TYPE3(LR) option of MODEL statement), the significant interaction terms (at $p \leq 0.10$) will be maintained in the model.

The maximum likelihood estimates of model coefficients (with associated standard error, degrees of freedom, Wald Chi-square statistic and p-value) will be presented for the final model along with the hazard ratios and 95% confidence intervals.

A single vertical bar graph will be presented showing the hazard ratios and 95% CIs (in favour of diosmectite or Placebo) from the separate individual models (i.e., each model containing a single covariate along with terms for treatment).

The hazard ratio and 95% CI from the overall final multivariate model will also be included in the above mentioned figure. For any covariate where the treatment by

covariate interaction is significant in the final multivariate model, the hazard ratio for treatment within each level of the covariate will be shown.

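### Step 2 of the exploratory Cox selection can call pathogen factors linked because untested subjects share a missing level, not because the pathogens are associated (minor)

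*SAP*

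**What the plan says.** The protocol (10.4.5) says that a Cox model will be used to "assess the impact of other factors like season of randomisation, absence/presence of faecal pathogens on the treatment effect". SAP 3.2.1.1 (g) turns this into a three-step selection over the factors in Table 2.

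- **Coding.** Virology is "Positive (Rotavirus or Adenovirus or Norovirus) (reference), Negative (None) Not done/missing" and parasitology is "Positive (aemibiasis or Giardia/lamblia) (reference), Negative (None) Not done/missing". Bacteriology follows the same pattern. SAP 3.2.18 applies the third level when no test of a panel has a result.
- **Source.** SAP 1.3.2.3: "One faecal sampling for microbiological examination will be collected as soon as possible after inclusion". It serves virology, bacteriology and parasitology alike.
- **Step 1.** Each factor is fitted with treatment in its own Cox model and goes forward if the Wald p-value is at most 0.20.
- **Step 2.** The factors retained are tested pairwise at 0.001. Two continuous factors use Pearson correlation. For mixed pairs, Spearman's "correlation coefficient will be used and for categorical variables a Chi2 test will be used". If independence fails, a choice is made on clinical and statistical relevance.
- **Step 3.** The selected factors enter a stepwise multivariate Cox model. Treatment interactions are examined for the terms that remain.

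The SAS code for Steps 1 and 3 is redacted. The visible text does not say that the missing level is left out of any of these tests.

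**The concern.** Step 2 is meant to detect factors that carry the same information. For two pathogen panels, the relevant question is whether a positive result on one goes with a positive result on the other. The three-level chi-square also asks whether subjects untested on one panel are untested on the other. With one sample feeding all panels, the answer to that second question is largely fixed by design, and it can dominate the statistic.

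The pair is then declared linked and someone must choose between the two factors. Interactions are examined only for terms left in the multivariate model, so a panel set aside at this point also loses its interaction test there.

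Step 1 has a related weakness. If its test covers all levels of the factor, a panel can be selected because untested subjects recover at a different rate, with no difference between Positive and Negative.

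The Spearman rule has a separate fault. Table 2 has one factor without categories (the watery-stool count) and six categorical factors, so there are six mixed pairs. Four of them involve an unordered factor with three or more levels: country and the three panels. A rank correlation with such a factor depends on how its levels happen to be numbered.

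**Working it through.** **Inputs.** N comes from SAP 1.2.1 ("854 subjects will be randomised to one of the two treatment groups") and SAP 1.3.4 ("363 evaluable subjects per treatment group (726 in total) will be required"). The 0.001 level and the chi-square test come from Step 2. A 3x3 table has 4 df, with critical value 18.47. The documents give neither the number of untested subjects nor the positivity rates. Assumed here: 1 to 85 subjects untested on both panels, positivity 3% to 30%, and independent results among tested subjects.

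**1. The plan's own figures.** SAP 1.3.4 is based on "Assuming a median time to recovery of 55 hours in the active group and 70 hours in the placebo group". Under exponential times the hazard ratio is 70/55 = 1.273. Schoenfeld's formula gives 540 events and Freedman's 546. Dividing by 0.75 (assumed efficiency of Gehan-Wilcoxon against log-rank under proportional hazards) gives 720 and 728, against 726 stated. Inflation: 726/(1 - 0.15) = 854.1, against 854. The plan states no figure for the Step 2 test beyond its threshold.

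**2. All missingness shared.** Let j subjects be untested on both panels and none on only one. The parts of the Pearson statistic for j = 2 are:
- shared missing cell: expected j²/N = 4/854 = 0.00468, contribution (2 - 0.00468)²/0.00468 = 850.00
- empty cells (missing on one panel, tested on the other): 2 x j(N - j)/N = 2 x 2 x 852/854 = 3.99
- tested block: j²/N = 0.005

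The total is 854.0 = N, p = 1.5e-183. The total is N for any j and any positivity rate; at N = 726 it is 726 (p about 8e-156).

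**3. Small-count check.** An expected count near 0.005 is too small for the Pearson approximation, so other tests were applied.
- Exact test of missing against tested: p = 1/C(854, j). For j = 1 this is 1/854 = 0.0012, which does not cross 0.001. For j = 2 it is 1/364,231 = 2.7e-6, which does.
- Likelihood ratio: G = 2[j ln(N/j) + (N - j) ln(N/(N - j))]. For j = 1, G = 15.5, p = 0.0038. For j = 2, G = 2[2 ln 427 + 852 ln(854/852)] = 28.2, p = 1e-5.

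**4. Some subjects missing one panel only.** Let d further subjects miss each panel alone, and let m = j + d. With independence otherwise, the 3x3 statistic is N x [(jN - m²)/(m(N - m))]².

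| Shared j | One-panel-only d | Chi-square | p |
|---|---|---|---|
| 1 | 5 | 22.1 | 0.0002 |
| 1 | 6 | 15.7 | 0.003 |
| 2 | 10 | 20.5 | 0.0004 |
| 2 | 11 | 16.9 | 0.002 |
| 2 | 20 | 3.8 | 0.43 |
| 5 | 21 | 23.8 | 9e-5 |
| 43 | 85 | 40.9 | 3e-8 |

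Example, j = 2 and d = 10: (2 x 854 - 144)/(12 x 842) = 0.1548, and 854 x 0.1548² = 20.5. An exact test is stricter: for j = 2 and d = 5, the hypergeometric probability of two or more shared, with both margins 7 out of 854, is 0.0012.

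**5. Positive versus Negative only.** Without the missing level, the constructed independent tables give chi-square of about 0 (p from 0.85 to 1.0). In 3,000 simulated trials with positivity 30% and 20% and no missing level, 0.07% gave p < 0.001, close to the nominal 0.1%. With one subject untested on both panels, 100% did so by the Pearson test.

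**6. Spearman.** Six countries can be numbered in 6! = 720 ways. As an illustration only, simulated over-dispersed counts were used with equal countries and assumed country means, two data sets per setting. With means over 5 to 7.5, Kruskal-Wallis p was 3e-9 and 2e-11, yet 65% and 62% of numberings were declared independent at 0.001. With means over 4 to 9, p was 4e-28 and 1e-22, and 39% and 46% were. The percentages depend on the assumed means; the dependence on numbering does not.

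**The case against.** The case against giving this weight is substantial, and most of it stands.

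- **A reader might infer that a single untested subject is enough.** It is enough only by the Pearson approximation with an expected count near 0.001. The exact and likelihood-ratio tests do not cross 0.001 for one subject.
- **Missingness may differ by panel.** The schedule of assessments lists virological results on a separate row, so one-panel gaps are plausible, and the table above shows that enough of them remove the signal.
- **A reader might infer that one or two pathogen factors are bound to be dropped.** Step 2 sees only factors that passed Step 1. Two could be lost only if all three passed. The SAP speaks of a choice, which implies setting a factor aside without saying so, and a statistician who saw the cause could use that discretion well.
- **A reader might infer that the protocol's pathogen assessment would go undone.** It would not. SAP 3.2.1.1 (g) fits a Cox model with treatment for each panel, plots Kaplan-Meier curves by level and shows the single-factor hazard ratios. Each panel is a pre-specified subgroup (3.2.18), and 3.2.1.1 (d) and (e) add sensitivity analyses for parasitology and bacteriology.
- **Redaction.** The code might handle the missing level differently, and that Step 1 tests all levels jointly is an inference.
- **Overlap is what Step 2 is for.** If all missingness is shared, the missing columns do coincide in Step 3. But this aliases only a redundant missing coefficient. The Positive-versus-Negative contrasts stay estimable, so it is no reason to discard a panel.

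What remains is that the rule as visibly written measures the wrong thing for these pairs, and that Spearman has no defined value for an unordered factor.

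**Conclusion.** The point holds as a minor one. When at least two subjects lack a sample and few miss only one panel, Step 2 declares any two pathogen factors from Step 1 linked, whatever the pathogens do: chi-square about 854 at N = 854, and exact p of about 3e-6 for two subjects. It then hands the multivariate model and its interaction tests a discretionary choice that rests on shared missingness.

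This assumes that the missing level stays in the Step 2 test, as the visible text implies, and that missingness is mostly shared. The documents give no count of untested subjects. How many one-panel gaps are tolerated depends on the number shared: with two shared, the Pearson signal is lost at 11 per panel, but with 43 shared it survives 85.

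SAP 3.1.4 reserves confirmatory status for the primary ITT analysis, and the selection is described as exploratory. The Gehan-Wilcoxon test, the Kaplan-Meier medians, the single-factor models and the pathogen subgroups do not depend on Step 2.

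**What to change.** In SAP 3.2.1.1 (g):

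1. **Step 1.** For the three pathogen factors, base selection on the Positive-versus-Negative contrast (1 df).
2. **Step 2, pathogen pairs.** Run the check on Positive versus Negative only, in subjects with results on both panels.
3. **Step 3.** Keep the panel-specific missing level, so that subjects missing one panel stay in the model. A single common indicator for no stool result is tempting, but it would leave those subjects without a code. State that for subjects with no sample the redundant missing coefficient may be aliased and is not interpreted.
4. **Step 2, mixed pairs.** For the watery-stool count against country or a pathogen panel, replace Spearman by a Kruskal-Wallis test with the correlation ratio (eta).

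The cost is a few lines of SAP text and small programming changes, with no new data. The only statistical price is slightly fewer subjects in the Step 2 check. If the redacted code already excludes the missing level, a sentence saying so would settle that part.

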3.2.1.2 Secondary efficacy analysis

The analysis regarding secondary efficacy endpoints will be performed on the ITT population. Supportive analysis using PP population will be carried out if more than 10% of subjects are excluded from ITT set.

Rules for handling incomplete dates and times recorded on the DEB are described in section 3.2.3.2.

(a) Abdominal pain intensity per 12-hour period

Intensity of abdominal pain per 12-hour period will be summarized by treatment group (an absence of pain will be considered as value zero).

Considering the ordinal nature of the outcome, difference between diosmectite and placebo will be studied by fitting a cumulative logit model assuming an ordered multinomial response distribution. The model will include treatment group as fixed effects and a random intercept effect. Contrasts between diosmectite and placebo will be given in term of odds ratios (modelling the probabilities to obtain higher scores of pain intensity). The model will be performed for each time point (12-hour period) separately (see SAS Syntax below).

CCI
[Redacted]

(b) Time from diarrhoea onset to recovery

This endpoint is a time to event endpoint which will be analysed using the same methodology as for the primary efficacy endpoint. The date and time of diarrhoea onset will be the start date and time of diarrhoea onset as recorded from the "History

of current acute diarrhoea episode” eCRF section. Subjects will be censored using the same rules as defined for the primary endpoint.

(c) Time from diarrhoea onset to the first formed stool.

This endpoint is a time to event endpoint which will be analysed using the same methodology as for the primary efficacy endpoint.

(d) Time from the 1st study treatment intake to the last watery stool.

This endpoint is a time to event endpoint which will be analysed using the same methodology as for the primary efficacy endpoint.

(e) Number of stools, per 12-hour period.

Number of stools per 12-hour period (0-12h, 12-24h, 24-36h...) will be computed by summing the number of stools as recorded in the DEB by the subject using the time (24-hour clock) of visit to restrooms. The number of stools per 12-hour period will then summarized by treatment group. From first to last intake, if no stool is reported in the diary at a specific time interval, the number of stools at the considered 12-hour period will be considered as zero.

Any stool with a missing evaluation consistency should be counted in the total number of stools per 12-hour period (if time of stool is not missing).

Any stool with a missing time, with a consistency evaluation and which is embedded within the same time interval will be counted in the number of stools for the considered time interval. The number of stools per 12-hour period during the post baseline period will be analysed with an analysis of covariance (ANCOVA) method with repeated measurements. The model will include number of stools 24 hours before randomisation (baseline) as covariate, treatment, time point (12-hour period until visit 3), the treatment by time point interaction as fixed effects and subject as random effect. The residual variance-covariance pattern will be fitted using an unstructured matrix (see SAS Syntax below). Adjusted means, 95% CIs and corresponding p-values of differences between diosmectite and placebo, derived from the model, will be displayed globally and for each time point.

CCI

[REDACTED]

If the model fails to converge, only time intervals with a sufficient number of patients could be included in the model.

In the event of gross violations from the normality assumptions (identified using the shape of the distribution and QQ plots of change from baseline overall and by visit) or from the covariance model assumptions or in case of convergence criterion fails to be reached, a non-parametric analysis will be used instead (Mann-Wilcoxon-Mann-Whitney test (see SAS syntax below)) at each time point separately.

CCI
[REDACTED]
[REDACTED]
[REDACTED]
[REDACTED]
[REDACTED]
[REDACTED]

In addition the cumulative number of stools per 12-hour period will be presented graphically using barcharts of means (\pm SEM) on observed values at each time point by treatment group.

(f) Number of watery stools, per 12-hour period.

The same analysis as described above will be performed for number of watery stools (corresponding to type 6 or 7). The model will include, as fixed effects, number of watery stools 24 hours before randomisation, treatment, time point (12-hour interval) and the treatment by time point interaction effect.

(g) Percentage of subjects with associated symptoms such as nausea, vomiting, abdominal pain and anal irritation, per 12-hour period.

The proportion of subjects with at least one associated symptom will be displayed per treatment group and per 12-hour period, using data retrieved from the DEB for post baseline values and using data retrieved from the eCRF for baseline value (Presence of associated symptoms during the last 24 hours from the “History of current acute diarrhoea episode” page). Same results will be displayed for each symptom separately: nausea, vomiting, abdominal pain and anal irritation. To assess the treatment effect at each 12-hour period on associated symptoms overall and on each symptom separately, a non-linear mixed model will be used including treatment and status of subjects at baseline (With or without associated symptoms), time-point and treatment by time-point interaction as fixed effects and number of watery stools during 24h prior inclusion as covariate (see SAS Syntax below).

CCI
[REDACTED]
[REDACTED]
[REDACTED]
[REDACTED]
[REDACTED]
[REDACTED]
[REDACTED]
[REDACTED]
[REDACTED]

In addition the percentage of subjects (with at least associated symptom and for each symptom separately) per 12-hour period will be presented graphically using barcharts at each time point by treatment group.

3.2.2 *Safety*

All safety data will be included in the data listings and summary tables will be based on the safety population.

